## 9. ADVERSE EVENTS

# 9.1. Adverse Event Reporting

This study will be conducted in accordance with the European Medicines Agency (EMA) "Guidance on the Management of Clinical Trials During the COVID-19 (Coronavirus) Pandemic" as well as the FDA Guidance for Industry, Investigators, and Institutional Review Boards "Conduct of Clinical Trials of Medical Products During the COVID-19 Public Health Emergency."

#### 9.1.1. Definitions of an Adverse Event

An AE is defined as any untoward medical occurrence in a clinical study patient administered zetomipzomib or placebo, which does not necessarily have a causal relationship with this treatment. An AE can therefore be any unfavorable and unintended sign (including a clinically significant abnormal laboratory finding), symptom, or disease temporally associated with the use of zetomipzomib or placebo, whether or not it is related to the treatment. This includes an exacerbation of pre-existing conditions or events, intercurrent illnesses, drug interaction, or the significant worsening of the indication under investigation that is not recorded elsewhere in the eCRF under specific efficacy assessments. Anticipated fluctuations of pre-existing conditions, including the disease under study, that do not represent a clinically significant exacerbation or worsening need not be considered as an AE.

It is the responsibility of the Investigator to document all AEs that occur during the study. AEs will be elicited by asking the patient a nonleading question such as, "Have you experienced any new or changed symptoms since we last asked/since your last visit?" AEs should be reported on the appropriate page of the eCRF.

# 9.1.2. Assessment of Severity

Severity of AEs will be graded according to the National Cancer Institute-Common Terminology Criteria for Adverse Events (NCI-CTCAE) Version 5.0. If a new version is released during the conduct of the study, the impact will be assessed, and a determination will be made regarding which version to follow. If there is a change in severity of an AE, it must be recorded as a separate event.

## 9.1.3. Assessment of Causality

AEs will be deemed related to zetomipzomib or placebo unless clearly unrelated to zetomipzomib or placebo. The Investigator will assess the causal relationship between zetomipzomib or placebo and the AE. One of the categories listed in Table 4 should be selected based on medical judgment, considering the definitions and all contributing factors.

**Table 4:** Adverse Event Causality Categories

Related	A clinical event, including clinically significant laboratory test abnormality, that occurs in a plausible time relationship to zetomipzomib or placebo administration, and that concurrent disease or other drugs or chemicals cannot explain. The response to withdrawal of the zetomipzomib or placebo (dechallenge a ) should be clinically plausible. The event must be definitive pharmacologically or phenomenologically, using a satisfactory rechallenge b procedure, if necessary.
Unrelated	A clinical event, including clinically significant laboratory test abnormality, with little or no temporal relationship to zetomipzomib or placebo administration. May have negative dechallenge a and rechallenge b information. Typically explained by extraneous factors (eg, concomitant disease, environmental factors, or other drugs or chemicals).

<sup>a Dechallenge: upon discontinuation of zetomipzomib or placebo suspected of causing an AE, the symptoms of the AE disappear partially or completely, within a reasonable time from zetomipzomib or placebo discontinuation (positive dechallenge), or the symptoms continue despite withdrawal of the zetomipzomib or placebo (negative dechallenge). Note that there are exceptions when an AE does not disappear upon discontinuation of zetomipzomib or placebo, yet drug-relatedness clearly exists (eg, bone marrow suppression, fixed drug eruptions, or tardive dyskinesia).

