#### 6.1.3. Dose Modification Guidelines

#### 6.1.3.1. Dose Reduction

Patients who experience a treatment-related AE at the 60-mg dose of zetomipzomib or placebo will be permitted to undergo dose reduction to the 30-mg dose of zetomipzomib or placebo for subsequent doses at the discretion of the Investigator, in consultation with the Medical Monitor. Patients on the 30-mg dose are not able to have a dose reduction. Approval from the Medical Monitor should be obtained in advance of implementing dose reduction, when possible. After dose reduction is implemented, patients should remain on the reduced dose for at least 2 doses, after which re-escalation to the patient's originally assigned dose should be attempted/encouraged. If the original dose is not tolerated after re-escalation, a reduced dose may be continued for the remainder of the study at a minimum 30-mg dose of zetomipzomib or placebo, or re-escalation may be reattempted after written approval from the Medical Monitor. Any dose modifications should be documented in the electronic case report form (eCRF) as per Section 9.1.4.

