## 9.6. Unexpected Adverse Reactions

#### 9.6.1. Definition of an Unexpected Adverse Reaction

An unexpected adverse reaction is any untoward and unintended response that is related to the administration of zetomipzomib or placebo at any dose, which is not consistent with the applicable product information (eg, the Reference Safety information of the zetomipzomib Investigator's Brochure).

All suspected unexpected serious adverse reactions (SUSARs) will be subject to expedited reporting. The Sponsor or designee shall ensure that all relevant information about an SUSAR that is fatal or life-threatening is reported to the relevant competent authorities and IRB/IEC within 7 days after knowledge by the Sponsor of such a case and that relevant follow-up information is communicated within an additional 8 days. All other SUSARs will be reported to the relevant competent authorities and IRB/IEC within 15 days after knowledge by the Sponsor of such a case. All Investigators should follow SUSARs until the event is resolved or until, in the opinion of the Investigator, the event is stabilized or determined to be chronic. Post-study SUSARs that occur after the patient has completed the clinical study must be reported by the Investigator to the Sponsor.

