9.1.2. Relationship of Adverse Events to Study Drug

Adverse events will be classified as related to zetomipzomib or placebo or not related to zetomipzomib or placebo. Missing relationship status will be imputed as related.

The number and percentage of patients with at least one related TEAE will be summarized by treatment group and overall. Related TEAEs will be further summarized by SOC and PT.

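### Protocol 9.1.3 and its own Table 4 conflict on causality for any plausibly timed adverse event that has another possible cause

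*Protocol*

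**What the plan says.** Protocol 9.1.3 opens with a default that favours relatedness: "AEs will be deemed related to zetomipzomib or placebo unless clearly unrelated to zetomipzomib or placebo". The same paragraph then tells the investigator how to record the call: "One of the categories listed in Table 4 should be selected based on medical judgment, considering the definitions and all contributing factors".

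Table 4 offers two categories and nothing between them.

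- **Related** needs plausible timing, an event of a kind "and that concurrent disease or other drugs or chemicals cannot explain", and a clinically plausible response to withdrawal. It adds a certainty condition: "The event must be definitive pharmacologically or phenomenologically, using a satisfactory rechallenge" procedure, where one is needed.
- **Unrelated** describes an event "with little or no temporal relationship to zetomipzomib or placebo administration". It adds that dechallenge and rechallenge may be negative and that some outside factor, such as concomitant disease or another drug, is the typical explanation.

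SAP 9.1.2 uses the same two-way split without defining it further, and adds one rule: "Missing relationship status will be imputed as related".

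Other sections rest on the call. Protocol 9.6.1 defines an unexpected adverse reaction as "any untoward and unintended response that is related to the administration of zetomipzomib or placebo at any dose" that does not match the product information. Protocol 6.1.3.1 says: "Patients who experience a treatment-related AE at the 60-mg dose of zetomipzomib or placebo will be permitted to undergo dose reduction".

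**The concern.** The sentence puts the burden on showing that study drug was not involved. The Related row of the table puts it on showing that nothing else could have been. Two investigators who each follow 9.1.3 in good faith can therefore classify the same event differently, depending on which half they apply.

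This trial should produce such events. Under Protocol 3.1 all patients have active lupus nephritis and are to receive MMF or equivalent for 52 weeks, with tapered oral corticosteroids. The protocol acknowledges the overlap. Section 6.2.1.3 staggers MMF against the first study doses so that gastrointestinal effects can be told apart, and section 9.8 notes that severe and opportunistic infections are more frequent in lupus nephritis patients on chronic immunosuppressives. An infection, a cytopenia or nausea on study is an ordinary example.

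At stake is whether the word related means one thing across sites wherever the plan uses it for safety reporting or tabulation.

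**Working it through.** No arithmetic applies: the point depends on no rate, sample size or error level. The check sets the opening sentence of 9.1.3 beside the two Table 4 rows, by type of event.

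| Type of event | Opening sentence | Table 4, Related | Table 4, Unrelated |
|---|---|---|---|
| 1. Plausible timing, no other explanation (eg, injection site reaction) | Related | Can fit | Does not fit |
| 2. No temporal link, other explanation clear | Clearly unrelated, so not related | Does not fit | Fits |
| 3. Plausible timing, another explanation possible (eg, infection, cytopenia or nausea on MMF and corticosteroids) | Related, because not clearly unrelated | Barred: disease or another drug could explain it | Fits on the alternative cause, fails on timing |

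The two rules agree for types 1 and 2. For type 3 the sentence says related, the Related row excludes the event, and the Unrelated row fits only in part. An investigator who gives weight to the alternative-cause line of that row reaches the opposite answer to the sentence. One who gives weight to its timing line finds no category.

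Next, whether other text resolves type 3:

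- **Medical judgment.** It is to be exercised with the definitions in view, and the definitions are what conflict with the default.
- **Dechallenge and rechallenge.** Rechallenge applies only where needed, and the dechallenge footnote allows relatedness when an event persists after withdrawal. Both soften the evidence asked for. Neither lifts the bar on events that something else could explain.
- **Serious events.** Protocol 9.5.2 and 9.7 require permanent discontinuation once thrombotic microangiopathy or hypersensitivity is confirmed, so rechallenge cannot supply the definitive evidence there.
- **SAP 9.1.2.** Imputing a missing call as related agrees with the sentence but covers blanks only. A type 3 event left blank counts as related; the same event assessed under Table 4 may not.

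Last, where the call is used:

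- SUSAR classification, through the definition in Protocol 9.6.1.
- SAEs after the reporting period, which Protocol 9.2.2 asks for only when the investigator judges them related.
- The treatment-related condition for dose reduction in Protocol 6.1.3.1.
- The related rows and summaries in SAP 9.1.1, 9.1.2, 9.1.4, 9.1.5 and 9.1.6 (TEAEs, serious events, AESIs and opportunistic infections).

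**The case against.** The strongest reply is that the opening sentence already works as a tie-breaker. If a type 3 event does not fit Unrelated on timing, the default sends it to Related, and judgment does the rest. That is a sensible reading, but the plan does not state it, and the Related row says the reverse in terms. The reply supports the fix more than it removes the need for one.

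A reader might go further and infer that hardly any event in this trial could be called Related under Table 4, so that the related share could run from almost none to almost all. The documents do not support that. Protocol 1.2 describes the commonest adverse events as injection site reactions, which lupus, MMF or corticosteroids do not readily explain. Systemic injection reactions have a characteristic onset 8 to 24 hours after dosing (Protocol 9.5.1), although each symptom is recorded, and so assessed, separately. Under Protocol 9.4, new or worsening SLE manifestations are not recorded as adverse events unless serious. Having lupus and taking MMF also does not mean that either explains a particular event; the table is applied event by event. With no adverse event counts, no range can be derived.

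A reader might also infer that serious events would go unreported during the trial. They would not. Protocol 9.2.2 requires every SAE in the reporting period within 24 hours whatever its suspected cause, and Protocol 9.5 asks for Grade 3 or higher AESIs on the same clock regardless of relatedness. AESIs are identified in SAP 9.1.5 from the eCRF or preferred terms, not from causality. The primary safety endpoint (Protocol 2.2.4) and the main TEAE and exposure-adjusted tables are all-causality. Calls are made blind to active versus placebo, so inconsistency need not favour an arm. Dose reduction also involves investigator discretion and the Medical Monitor. All of this stands and limits the reach of the point; none of it removes the contradiction.

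**Conclusion.** The contradiction is real and confined to one class of event: plausible timing with a possible alternative cause. For that class Protocol 9.1.3 either gives opposite answers or leaves the event without a category, and the SAP does not settle it.

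The size cannot be put as a number. That such events will occur rests on the design (active lupus nephritis plus MMF and corticosteroids in all patients) and on the protocol's own remarks about overlapping effects, not on any observed rate.

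The consequence is inconsistent classification in the four uses listed above. Whether sites would in practice under-call relatedness is conjecture, since it depends on which half of the section they follow. This should be corrected because the wording feeds safety reporting and is cheap to change; it does not threaten the efficacy analysis or the principal safety comparison.

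**What to change.** Reconcile Table 4 with the text of Protocol 9.1.3 and state that the default governs. Specifically:

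- Word Related so that a possible contribution from concurrent disease or another drug does not by itself exclude it.
- Remove from Related the condition that nothing else can explain the event and the condition that it be definitive.
- Tell sites, by memo, how to classify a plausibly timed event with a competing cause.

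The dose-reduction passage in Protocol 6.1.3.1 uses the same term and must be read consistently with the reconciled definition; no dosing rule is proposed here. SAP 9.1.2 already agrees with the default and needs no change.

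The cost is protocol table wording and a site communication, with no new data collection. The downside is that counts of related events and of expedited reports may rise.

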# 9.1.4. Action Taken with Regard to Zetomipzomib or Placebo

The Investigator will describe the action taken with zetomipzomib or placebo in the appropriate section of the eCRF, as one of the following:

- None
- Dose stopped
- Dose temporarily interrupted
- Dose reduced (with written approval from the Medical Monitor)
- Other (specify)

## 9.1.5. Follow-up of Adverse Events

AEs are intended to be collected, according to the procedures outlined, from the time of informed consent and continuing for 30 days following the last dose of zetomipzomib or placebo or the EOS visit, whichever occurs later.

All Investigators should follow patient AEs until the event is resolved or until, in the opinion of the Investigator, the event is stabilized or determined to be chronic. Details of AE resolution must be documented in the eCRF.

# 9.1.6. Documenting and Reporting of Adverse Events

AEs (including SAEs) should be reported and documented on the relevant eCRF pages in accordance with the procedures outlined. The following data should be documented for each AE:

<sup>b Rechallenge: upon readministration of zetomipzomib or placebo suspected of causing an AE in a specific patient in the past, the AE recurs upon exposure (positive rechallenge), or the AE does not recur (negative rechallenge). AE=adverse event.

- Diagnosis, or description of the symptoms if a diagnosis is not established
- Classification of 'serious' or 'not serious'
- Severity
- Date of first occurrence and date of resolution (if applicable)
- Action taken with regard to zetomipzomib or placebo
- Outcome of the event (unknown, recovered, not yet recovered, recovered with sequelae, death [with date and cause reported])

#### 9.2. Serious Adverse Events

#### 9.2.1. Definition of a Serious Adverse Event

An SAE is any untoward medical occurrence or effect that, at any dose:

- Results in death
- Is life-threatening
  (An AE is life-threatening if the patient was at immediate risk of death from the event as it occurred, ie, it does not include a reaction that might have caused death if it had occurred in a more serious form.)
- Requires or prolongs inpatient hospitalization
  (Complications occurring during hospitalization are AEs and are considered SAEs if
  they cause prolongation of the current hospitalization. Hospitalization for elective
  treatment of a pre-existing non-worsening condition is not, however, considered an
  AE. The details of such hospitalizations must be recorded on the medical history or
  physical examination page of the eCRF.)
- Results in persistent or significant disability/incapacity
  (An AE is incapacitating or disabling if it results in a substantial and/or permanent disruption of the patient's ability to carry out normal life functions.)
- Results in a congenital anomaly/birth defect

Important medical events that may not result in death, be life-threatening, or require hospitalization may be considered serious when, based upon appropriate medical judgment, they may jeopardize the patient and may require medical or surgical intervention to prevent one of the outcomes listed in this definition. Examples of such medical events include allergic bronchospasm requiring intensive treatment in an emergency room or at home, blood dyscrasias or convulsions that do not result in inpatient hospitalization, or the development of drug dependency or drug abuse.

#### 9.2.2. Serious Adverse Event Reporting and Documentation Requirements

An SAE must be reported (see Section 9.1.6) by the Investigator if it occurs from the time of signed consent through 30 days after the last dose of zetomipzomib or placebo or the EOS visit, whichever occurs later, whether or not the SAE is considered to be related to treatment. After the

reporting period, SAEs should only be reported if the Investigator assesses the event to be related to study treatment.

Every SAE that occurs during the reporting period regardless of suspected causality must be reported by the Investigator in the electronic data capture (EDC) system (AE/SAE eCRF) within 24 hours from the time the Investigator becomes aware of the SAE. If there are any issues with EDC, a completed paper SAE report form should be emailed or faxed within 24 hours for the attention of the Project Manager (see Study Personnel page). Additional source documents can be requested, if deemed necessary.

The Investigator should not wait for additional information to fully document the event before notification of an SAE, though additional information may be requested. Where applicable, information from relevant laboratory results, hospital case records, and autopsy reports should be obtained. Follow-up information should be submitted in the same way as the original SAE report.

Instances of death, congenital abnormality, any SAEs, or an event of such clinical concern as to influence the overall assessment of safety, if brought to the attention of the Investigator at any time after cessation of zetomipzomib or placebo administration and considered by the Investigator to be related to participation in this study, should be reported to the Medical Monitor and to

The Sponsor and/or designee will promptly notify all relevant Investigators and the regulatory authorities of findings that could adversely affect the safety of patients, impact the conduct of the study, or alter the IDMC (or appropriate alternative)/Institutional Review Board (IRB)/Independent Ethics Committee (IEC) approval/favorable opinion of the study. In addition, the Sponsor or designee will expedite the reporting of all adverse reactions that are both serious and unexpected to all concerned Investigators, to the IDMC (or appropriate alternative)/IRBs/IECs where required, and to relevant regulatory authorities.

For SAEs that have been reported in the zetomipzomib development program, refer to the most current zetomipzomib (KZR-616) Investigator's Brochure.

## 9.3. Pregnancy Reporting

Pregnancy occurring in female patients or female partners of male patients participating in the study or during a clinical investigation must be reported to the Report Form within 24 hours and entered into the EDC. The outcome of a pregnancy should be followed up carefully, and any abnormal outcome for the mother or the child should be reported. Infants should be followed for a minimum of 8 weeks, and all findings should be reported to via the Pregnancy Report Form. Zetomipzomib or placebo is to be discontinued immediately upon Investigator knowledge of the pregnancy in a female patient or a female partner of a male participant and reported as per Section 8.1.2.

If the outcome of the pregnancy meets a criterion for immediate classification as an SAE (ie, spontaneous abortion [for which any congenital anomaly detected in an aborted fetus is to be documented], stillbirth, neonatal death, or congenital anomaly), the Investigator should follow the procedures for expedited reporting of SAEs as outlined in Section 9.2.2.

Any SAE experienced by a subject during pregnancy must be reported as an SAE.

Full details will be recorded on the withdrawal page of the eCRF, or an SAE report will be completed if the patient has completed the study.

## 9.4. New or Worsening Disease Manifestations

New or worsening manifestation(s) of SLE should not be recorded as AEs unless they are assessed as serious. New or worsening manifestation(s) of SLE should be captured on the clinical lupus disease assessments (see Appendix 3 and Section 7.2.2.4).

### 9.5. Adverse Events of Special Interest

An adverse event of special interest (AESI) is one that is of scientific and medical concern specific to the Sponsor's product or program, for which ongoing monitoring and rapid communication by the Investigator to the Sponsor can be appropriate, regardless of the seriousness, expectedness, or relatedness of the AE to the administration of zetomipzomib or placebo.

SIRs and thrombotic microangiopathy have been identified as AESIs. Any Grade 3 or higher AESIs should be reported within 24 hours using the AE eCRF.

## 9.5.1. Systemic Injection Reactions

In clinical studies of zetomipzomib, SIRs associated with subcutaneous injections have been reported, consisting of 1 or more of the following signs/symptoms: hypotension, tachycardia, nausea, vomiting, dizziness, headache, pyrexia, rigors, and/or chills. The events are associated with an acute phase-like response, including leukocytosis and elevated C-reactive protein, occur within 8 to 24 hours after dosing, and usually resolve within 48 hours of dosing. While most commonly associated with an initial subcutaneous dose of zetomipzomib 60 mg and reduced in frequency when initially dosed with 30 mg, any or all of these events could occur with lower doses of zetomipzomib or with subsequent higher doses of zetomipzomib. The events are similar to those described for infusion-related reactions observed with the currently approved proteasome inhibitor carfilzomib, which generally occur in the first cycle of dosing.

In reporting TEAEs related to zetomipzomib or placebo tolerability, terms such as the NCI-CTCAE terms of "infusion-related reaction," "cytokine release syndrome," "acute infusion reaction," or "allergic or hypersensitivity reaction" should not be used. Instead, each sign or symptom should be recorded as an individual TEAE. If multiple signs or symptoms occur with a given systemic injection-related event, each sign or symptom should be recorded separately with its own level of severity.

Management of these symptoms is described in Section 6.1.2.

